7. PRIMARY STATISTICAL ANALYSES

7.1. Pharmacokinetic Analyses

7.1.1. Overview of Planned Pharmacokinetic Analyses

The PK analyses will be based on the PK Population for plasma PK concentrations, and PK Parameter Population for plasma/urine PK parameters, unless otherwise specified.

[Table 3](#) provides an overview of the planned analyses, with full details being presented in [Appendix 11: List of Data Displays](#).

Table 3 Overview of Planned Pharmacokinetic Analyses

Display Type	Untransformed							Log-Transformed						
	Stats Analysis			Summary		Individual		Stats Analysis			Summary		Individual	
	T	F	L	T	F	F	L	T	F	L	T	F	F	L
Plasma PK Concentrations				Y	Y ^[1] ^[2]	Y ^[1]	Y						Y ^[1] ^[2]	Y ^[1]
Urine PK Concentrations				Y	Y ^[1] ^[2]	Y ^[1]	Y						Y ^[1] ^[2]	Y ^[1]
Plasma PK Parameters	Y	Y		Y			Y	Y			Y			Y
Urine PK Parameters ^[3]				Y			Y				Y			

NOTES:

- T = Table, F = Figure, L = Listing, Y = Yes display generated.
- Stats Analysis = Represents TFL related to any formal statistical analyses (i.e. modelling) conducted.
- Summary = Represents TFL related to any summaries (i.e. descriptive statistics) of the observed raw data.
- Individual = Represents FL related to any displays of individual subject observed raw data.

^[1] Linear and Semi-Log plots will be created on the same display.

^[2] Separate mean and median plots will be generated.

^[3] Parts 1a, 2 and 3 only.

7.1.2. Drug Concentration Measures

Refer to [Appendix 3: Data Display Standards & Handling Conventions \(Section 3 Reporting Process & Standards\)](#).

7.1.3. Pharmacokinetic Parameters

7.1.3.1. Deriving Pharmacokinetic Parameters

- Refer to [Appendix 3: Data Display Standards & Handling Conventions \(Section 3 Reporting Process & Standards\)](#).
- The PK parameters will be calculated by standard non-compartmental analysis according to current working practices and using Phoenix WinNonlin Version 6.2.1 or higher.

- All calculations of non-compartmental parameters will be based on actual sampling times.
- Pharmacokinetic parameters described in [Table 4](#) will be determined from the plasma concentration-time data, as data permits.
- Pharmacokinetic parameters described in [Table 5](#) will be determined from the urine concentration data, as data permits.

Table 4 Derived Plasma Pharmacokinetic Parameters

Parameter	Parameter Description
AUC(0-t)	Area under the concentration-time curve (AUC) from time 0 (predose) to time of the last quantifiable concentration, to be calculated using the linear trapezoidal rule for each incremental trapezoid and the log trapezoidal rule for each decremental trapezoid.
AUC(0-∞)	Area under the concentration-time curve from time 0 (predose) extrapolated to infinite time, calculated as: $AUC(0-\infty) = AUC(0-t) + C(t) / \lambda z$ where C(t) is the last observed quantifiable concentration.
%AUCex	The percentage of AUC (0-∞) obtained by extrapolation (%AUCex) will be calculated as: $[AUC(0-\infty) - AUC(0-t)] / AUC(0-\infty) \times 100$
Cmax	Maximum observed concentration, determined directly from the concentration-time data.
Tmax	Time to first occurrence of Cmax
tlag	Lag time before observation of drug concentrations in sampled matrix
t½	Terminal phase half-life will be calculated as: $t\frac{1}{2} = \ln 2 / \lambda z$
Frel	Relative bioavailability of drug, calculated as: $F_{rel} = [AUC(0-\infty)_{tablet}] / [AUC(0-\infty)_{capsule}] \text{ (Part 1a only)}$
λz	Terminal-phase rate constant
DNAUC(0-t)	Dose normalized area under the concentration-time curve from time 0 (predose) to time of the last quantifiable concentration (Part 2 and Part 3 for use in the pooled analysis with Part 2), to be calculated as $DNAUC(0-t) = AUC(0-t) / Dose$
DNAUC(0-∞)	Dose normalized area under the concentration-time curve from time 0 (predose) extrapolated to infinite time (Part 2 and Part 3 for use in the pooled analysis with Part 2), calculated as $DNAUC(0-\infty) = AUC(0-\infty) / Dose$
DNCmax	Dose normalized maximum observed concentration (Part 2 and Part 3 for use in the pooled analysis with Part 2), to be calculated as

Parameter	Parameter Description
	DNCmax = Cmax / Dose

NOTES:

- Additional parameters may be included as required.

Table 5 Derived Urine Pharmacokinetic Parameters (Parts 1a, 2, and 3 only)

Parameter	Parameter Description
Ae total	Total unchanged drug (total amount of drug excreted in urine), calculated by adding all the fractions of drug collected over all the allotted time intervals
Ae(t1-t2)	Amount of drug excreted in urine in a time intervals for predose, 0 to 2 hours, 2 to 4 hours, 4 to 6 hours, 6 to 8 hours, 8 to 12 hours, 12 to 24 hours, 24 to 36 hours, and 36 to 48 hours.
AUC(0-12)	Area under the urine concentration-time curve over time 0 (predose) to 12 hours after dosing. The AUC will be calculated by the linear trapezoidal rule based on the urine concentration data from each collection interval versus the corresponding urine collection interval.
AUC(0-24)	Area under the urine concentration-time curve over time 0 (predose) to 24 hours after dosing. The AUC will be calculated by the linear trapezoidal rule based on the urine concentration data from each collection interval versus the corresponding urine collection interval.
AUC(0-48)	Area under the urine concentration-time curve over time 0 (predose) to 48 hours after dosing. The AUC will be calculated by the linear trapezoidal rule based on the urine concentration data from each collection interval versus the corresponding urine collection interval.
fe%	Percentage of the given dose of drug excreted in urine, calculated as: $fe\% = (Ae\ total / Dose) \times 100$
CLr	Renal clearance of drug, calculated as: $CLr = Ae\ total / AUC(0-t)$

NOTES:

- Additional parameters may be included as required.

7.1.3.2. Statistical Analysis of Pharmacokinetic Parameters

The following PK statistical analyses will only be performed if sufficient data is available (i.e. if subjects have well defined plasma profiles).

Pharmacokinetic Statistical Analyses
Endpoint(s)

 Plasma primary PK endpoints include AUC(0-∞), AUC(0-t) and Cmax of gepotidacin, as data permit
Model Specification

 The log-transformed AUC(0-∞), AUC(0-t), and Cmax values for gepotidacin will be analyzed

Pharmacokinetic Statistical Analyses

separately using a mixed effects model as appropriate to the study design, fitting fixed effect terms for sequence, period, and regimen, and treating subject within sequence as a random effect. Point estimates and 90% confidence intervals (CIs) for the differences of interest (RC tablets and HSWG tablets versus capsules) will be constructed using the residual variance

- In the optional food effects study in Part 1b, the log-transformed AUC(0-∞), AUC(0-t), and Cmax values for gepotidacin will be analyzed separately using a mixed effects model as appropriate to the study design, fitting fixed effect terms for sequence, period, and regimen, and treating subject within sequence as a random effect. Point estimates and 90% CIs for the differences of interest (tablet formulation under fasted and fed conditions) will be constructed using the residual variance. The ratio of geometric mean and 90% CIs of ratio will be obtained by exponentiation of the point estimates and 90% CIs for the difference on the natural logarithmic scale.
- For the bioavailability assessment, Tmax will be analyzed nonparametrically using the Wilcoxon signed-rank test to compute the point estimate and 90% CI for the median difference for each comparison of interest.
- In Part 2, dose proportionality will be evaluated for the dose-normalized (DN) PK parameters for gepotidacin: DNAUC(0-∞), DNAUC(0-t), and DNCmax. An analysis of variance (ANOVA) model with log transformed DN PK parameters [DNAUC(0-∞), DNAUC(0-t), and DNCmax] as dependent variable, dose group as a fixed effect and subject as a random effect will be used to estimate the DN geometric means of each dose, and the ratio of geometric means between two doses (3000 mg vs 1500 mg) with 90% CI for Part 2 subjects alone. Additionally, subjects in Part 2 (fasted) and Part 3 (fed) will be pooled together in an exploratory analysis to assess the dose proportionality between 3000 mg and 1500 mg. There would be evidence of dose proportionality if the 90% CI for the ratio of DN geometric means lies within the limits (0.80, 1.25).
- For Parts 2 and 3, PK parameters will be summarized based on pooled data (for the doses (1500 mg and 3000 mg).
- Additionally, for Part 3, dose proportionality in the Japanese fed cohort portion of the study will be evaluated by using the power model:

$$y = \alpha \times (\text{dose})^\beta$$

where y denotes the PK parameter being analyzed [AUC(0-∞), AUC(0-t), and Cmax]. Dose proportionality implies that $\beta = 1$ and will be assessed by estimating β along with its 90% confidence interval. The exponent, β , in the power model will be estimated by regressing the natural log-transformed PK parameter on natural log-transformed dose.

$$\text{Ln}(y) = \text{ln}(\alpha) + \beta * \text{ln}(\text{dose})$$

The power model will be fitted by restricted maximum likelihood (REML) using SAS Proc Mixed with subject as a random effect, or a fixed effect power model will be fitted. The mean slope will be estimated from the power model and the corresponding 90% confidence interval calculated. Point estimates and confidence intervals for the slope will be reported to 4 decimal places with no rounding.

Pharmacokinetic Statistical Analyses

 PK parameters for all subjects will be evaluated using the Grubbs' test [Grubbs, 1950] on the natural log-transformed PK parameters by treatment. For study parts where subjects have been identified as outliers, additional analyses will be performed with outliers excluded.
Model Checking & Diagnostics

 Refer to Appendix 9: Model Checking and Diagnostics for Statistical Analyses.
Model Results Presentation

 Statistical analysis by analysis of variance (ANOVA) will be presented in tabular format with geometric mean ratios between RC tablets and HSWG tablets versus capsules, and 90% CIs for the ratios of AUC(0-∞) and Cmax for gepotidacin. 
Example SAS Code:
 <pre>PROC MIXED; CLASS USUBJID TRTA TRTSEQP APERIOD; MODEL LOGPKPARM =TRTA TRTSEQP APERIOD /DDFM=KR; RANDOM USUBJID(TRTSEQP); LSMEANS TRTA; ESTIMATE 'B VS A' TRTA -1 1 0/CL ALPHA=0.1; ESTIMATE 'C VS A' TRTA -1 0 1/CL ALPHA=0.1;RUN;</pre> 
 Statistical analysis by ANOVA for the optional food effect (Part 1b) will be presented in tabular format with geometric mean ratios between tablet formulation under fasted and fed conditions, and 90% CIs for the ratios of AUC(0-∞) and Cmax for gepotidacin. 
Example SAS Code:
 <pre>PROC MIXED; CLASS USUBJID TRTA TRTSEQP APERIOD; MODEL LOGPKPARM =TRTA TRTSEQP APERIOD /DDFM=KR; RANDOM USUBJID(TRTSEQP); LSMEANS TRTA; ESTIMATE 'E VS D' TRTA -1 1/CL ALPHA=0.1; RUN;</pre> 
 Statistical analysis of Tmax will be analyzed nonparametrically using the Wilcoxon signed-rank test. 
Example SAS Code:
 <pre>PROC UNIVARIATE DATA=PK WILCOXON; VAR DIFF; /*DIFFERENCE OF AVAL FOR TREATMENT A-B */ CLASS TRTA; ODS OUTPUT =PVAL; RUN;</pre> 
 Statistical analysis by ANOVA for Part 2 and Part 3 will be presented in tabular format with geometric mean ratios between 3000-mg and 1500-mg (Part 2 alone and Parts 2 and 3 pooled), and 90% CIs for the ratios of DNAUC(0-t), DNAUC(0-∞) and DNCmax for gepotidacin. 
Example SAS Code:

Pharmacokinetic Statistical Analyses

```
ODS OUTPUT LSMEANS=LSM DIFFS=PAIR;
PROC MIXED DATA=PK3;
CLASS USUBJID DOSE;
MODEL LOGPP=DOSE/SOLUTION ALPHA=0.1 CL DDFM=KR;
RANDOM SUBJECT;
LSMEANS DOSE/PDIFF(CONTROL='1500 mg') ALPHA=0.1 CL;
RUN;
```

- Statistical analysis by REML for the Japanese food effect (Part 3) will be presented in tabular format to present the exponent β and 90% CI for the $AUC(0-\infty)$, $AUC(0-t)$, and C_{max} for gepotidacin in fed Japanese subjects.

Example SAS Code:

```
PROC MIXED;
CLASS SUBJECT;
MODEL LOGPKPARM =LOGDOSE /CL ALPHAS=0.1 SOLUTION;
RUN;
```

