10.9.1. Statistical Analysis Assumptions

Endpoint(s)	
• PK endpoints AUC(0-∞), AUC(0-t) and Cmax
Analysis	
• Mixed Effects

Assumptions:

- Model assumptions will be applied, but appropriate adjustments maybe made based on the data.
- The Kenward and Roger method for approximating the denominator degrees of freedom and correcting for bias in the estimated variance-covariance of the fixed effects will be used.

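### SAP 7.1.3.2: the example code for the Part 2/pooled and Part 3 dose-proportionality models does not fit the random subject effect that the text names, and the Part 3 fixed-effect alternative is undefined

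*SAP*

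**What the plan says.** All of this is in SAP 7.1.3.2 unless noted.

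- **Part 2 text.** In the ANOVA on log dose-normalized parameters, "dose group as a fixed effect and subject as a random effect will be used". Proportionality is supported if the 90% CI for the 3000 mg to 1500 mg ratio "lies within the limits (0.80, 1.25"). Parts 2 and 3 are also pooled for an exploratory version of the same comparison, with no separate model written out.
- **Part 2/pooled code.** One block serves both analyses. It has "CLASS USUBJID DOSE" and then "RANDOM SUBJECT".
- **Part 3 text.** The slope of the power model is estimated by REML "using SAS Proc Mixed with subject as a random effect, or a fixed effect power model will be fitted".
- **Part 3 code.** Introduced as the REML analysis, it lists SUBJECT in CLASS, and its model line is "MODEL LOGPKPARM =LOGDOSE /CL ALPHAS=0.1 SOLUTION". There is no RANDOM or REPEATED statement.
- **Part 1a and 1b code, for comparison.** It classifies USUBJID, uses "RANDOM USUBJID(TRTSEQP") and requests DDFM=KR.
- **SAP 10.9.1.** It lists the analysis as mixed effects and commits to Kenward-Roger: "The Kenward and Roger method for approximating the denominator degrees of freedom" will be used.

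**The concern.** Each active subject contributes two doses in Part 2 and three in Part 3. Protocol 4.4 justifies these small fixed-sequence cohorts by the saving in subjects over a parallel design, and that saving is realized only if subject is in the model.

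In the Part 2/pooled block, SUBJECT is not a CLASS variable. If it is numeric, PROC MIXED fits one random coefficient on the ID number. If it is character or absent, the step does not run. Neither gives a random intercept per subject.

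In the Part 3 block, three doses in one person are treated as independent. The open alternative in the text could mean subject as a fixed factor, which is valid, or no subject term, which is not. Nothing says which is meant or what triggers it, so the choice could be made after the data are seen.

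Dose proportionality is a secondary objective of both parts and is assessed on these 90% intervals.

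**Working it through.** Parts 2 and 3 are sized on feasibility (protocol 9.2.1), so there is no stated power or precision to reproduce. The check is what happens to the intervals.

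**Inputs**
- n = 10 subjects on active drug in each part (protocol 9.2.1), complete data.
- Part 3 doses 1500, 2250 and 3000 mg: Sxx = Σ(ln dose − mean)² = 0.2425 per subject.
- Total CVs from protocol 4.5, Table 6 (RC tablet, 1500 mg): fasted AUC(0-∞) 20.3%, fasted Cmax 24.7%, fed AUC(0-∞) 16.2%, fed Cmax 29.1%.
- Total log-scale variance st² = ln(1 + CV²).
- Within-subject correlation ρ is not in the documents. Assumed 0, 0.3, 0.5, 0.7, giving sw² = (1 − ρ)st² and sb² = ρ·st².

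**Formulas for the 90% half-width (log scale for the ratio)**
- Part 2 with subject: t(9) × √(2sw²/10), t(9) = 1.833. Without: t(18) × √(2st²/10), t(18) = 1.734.
- Part 3 slope with subject (random or fixed factor): t(19) × √(sw²/(10·Sxx)), t(19) = 1.729. Without: t(28) × √((sw² + (27/28)sb²)/(10·Sxx)), t(28) = 1.701. The residual term is [9(sw² + 3sb²) + 19sw²]/28.

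**Part 3, fed AUC, CV 16.2%, ρ = 0.5.** st² = 0.02591, sw² = sb² = 0.01296.
- With subject: 1.729 × √(0.01296/2.425) = 0.126, so 0.874 to 1.126 around an estimated slope of 1.
- Without: 1.701 × √(0.02545/2.425) = 0.174, so 0.826 to 1.174.
- For fed Cmax (CV 29.1%) the same steps give 0.776 to 1.224 and 0.691 to 1.309.

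**Part 2, fasted AUC, CV 20.3%, ρ = 0.5, observed ratio 1.** st² = 0.04038, sw² = 0.02019.
- With subject: 1.833 × √(0.004038) = 0.1165, so 0.890 to 1.124.
- Without: 1.734 × √(0.008076) = 0.1558, so 0.856 to 1.169.

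**Interval width relative to the model with subject (does not depend on CV in the first two rows)**

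| ρ | 0 | 0.3 | 0.5 | 0.7 |
|---|---|---|---|---|
| Part 3 slope, no subject | 0.98 | 1.17 | 1.38 | 1.77 |
| Part 2 ratio, no subject | 0.95 | 1.13 | 1.34 | 1.73 |
| Part 2 ratio, random coefficient on numeric ID | – | 1.11 | 1.32 | 1.68 |

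The last row is from 1,500 REML fits per correlation with IDs 1 to 10 and 18 df. Read with a numeric SUBJECT, the Part 2 code behaves almost as if subject were left out.

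**Chance that the Part 2 interval falls in 0.80 to 1.25 when the true ratio is 1 (40,000 simulated trials per setting)**

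| ρ | 0 | 0.3 | 0.5 | 0.7 |
|---|---|---|---|---|
| AUC, CV 20.3%, with subject | 49% | 73% | 88% | 99% |
| AUC, without | 54% | 62% | 68% | 78% |
| Cmax, CV 24.7%, with subject | 25% | 48% | 69% | 93% |
| Cmax, without | 27% | 32% | 37% | 46% |

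Repeat runs agree to about one percentage point. Simulated coverage of the nominal 90% interval for the Part 3 slope without subject is 90%, 95%, 97% and 99% across the four correlations.

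**The case against.** The strongest reply is that the model text governs and the code is labelled as an example. For Part 2 the text is clear, USUBJID against SUBJECT looks like a naming slip, and the numeric-ID outcome needs a numeric SUBJECT variable that no document shows; otherwise the step stops and someone corrects it. That is fair, and Part 2 alone would be a minor correction. The Part 3 block also needs editing before use, since it writes ALPHAS= where the other blocks have ALPHA=.

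For Part 3, code without a subject term can be read as the permitted fixed-effect branch, so it is less a flat contradiction than in Part 2. But that reading is the problem: one meaning of the branch gives the correct interval and the other does not. Correcting the option's spelling would leave code that runs and gives plausible output with subject still missing.

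The consequence is bounded. No formal hypothesis is tested, the pooled analysis is exploratory, the Part 3 slope has no acceptance limits, and the primary Part 1a code is consistent.

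The pass rates depend on borrowed CVs. They come from another study, whose tablet protocol 2.1 describes as the mesylate, while this study uses free base. With the 3000 mg capsule CVs in protocol Table 7 (31.5% AUC, 36.0% Cmax) and ρ = 0.5, the pass rates are about 39% against 9% for AUC and 24% against 3% for Cmax: lower throughout, with the same direction. The with-subject rates use a paired t with 9 df. A REML fit with subject variance bounded at zero gives 58 to 59% rather than 49% at ρ = 0 (AUC, CV 20.3%), with negligible difference from 0.5 upward.

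**Conclusion.** The concern holds and should be fixed. Neither code block fits the random subject effect that the text names, the Part 3 code omits the Kenward-Roger method that SAP 10.9.1 requires, and the fixed-effect power model has no definition or trigger anywhere in the SAP or in protocol 9.4.1.

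The conflict between text and code is certain. Its size is conditional on the assumed correlation: nothing material near 0, intervals 13 to 17% wider at 0.3, and 73 to 77% wider at 0.7. The direction is conservative. Unchanged point estimates hold only for complete data; if subjects miss a period, the ratio and slope can also differ between models. I computed no figures for the pooled analysis, which shares the Part 2 code.

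**What to change.** - **Part 2/pooled code:** replace `RANDOM SUBJECT` with `RANDOM USUBJID`.
- **Part 3 code:** `CLASS USUBJID; MODEL LOGPKPARM=LOGDOSE / SOLUTION CL ALPHA=0.1 DDFM=KR; RANDOM INTERCEPT / SUBJECT=USUBJID;`
- **Part 3 text:** replace the open alternative with a rule: if the random-effect model does not converge, subject will be fitted as a fixed CLASS effect. With complete data this gives the same slope interval as the random-subject model.

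The cost is a few example-code lines and one SAP sentence. No data, subjects or time are affected.

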7.1.4. Interim Analysis

7.1.4.1. Overview of Planned Analyses

Interim analysis is planned for Part 1a. Available PK data will be reviewed by the study team after completing Part 1a of the study to select the formulation for Part 1b, Part 2, and Part 3, and also to determine if the effect of food on the selected formulation needs to be studied (Part 1b).

[Table 7](#) provides an overview of the planned analyses, with full details of data displays being presented in [Appendix 11: List of Data Displays](#).

Plasma concentrations of gepotidacin will be subjected to PK analyses using noncompartmental methods. Based on the individual concentration time data the following parameters will be estimated:

Table 6 **Derived Plasma Pharmacokinetic Parameters**

Parameter	Parameter Description
AUC(0-t)	Area under the concentration-time curve from time 0 (predose) to time of the last quantifiable concentration, to be calculated using the linear trapezoidal rule for each incremental trapezoid and the log trapezoidal rule for each decremental trapezoid.

Parameter	Parameter Description
AUC(0-∞)	Area under the concentration-time curve from time 0 (predose) extrapolated to infinite time, calculated as: $\text{AUC}(0-\infty) = \text{AUC}(0-t) + C(t) / \lambda z$ where $C(t)$ is the last observed quantifiable concentration.
Cmax	Maximum observed concentration, determined directly from the concentration-time data.
Tmax	Time to first occurrence of Cmax
tlag	Lag time before observation of drug concentrations in sampled matrix
t½	Terminal phase half-life will be calculated as: $t\frac{1}{2} = \ln 2 / \lambda z$
Frel	Relative bioavailability of drug, calculated as: $F_{rel} = [\text{AUC}(0-\infty)_{\text{tablet}}] / [\text{AUC}(0-\infty)_{\text{capsule}}]$ (Part 1a only)

NOTES:

- Additional parameters may be included as required.

The log-transformed AUC(0-∞), AUC(0-t), and Cmax values for gepotidacin will be analyzed separately using a mixed effects model as appropriate to the study design, fitting fixed effect terms for sequence, period, and regimen, and treating subject within sequence as a random effect (Section 7.1.3.2).

For the bioavailability assessment, Tmax will be analyzed nonparametrically using the Wilcoxon signed-rank test to compute the point estimate and 90% CI for the median difference for each comparison of interest (Section 7.1.3.2).

Table 7 provides an overview of the planned interim analyses.

Table 7 Overview of Planned Interim Analyses

Display Type	Untransformed								Log-Transformed							
	Stats Analysis			Summary		Individual			Stats Analysis			Summary		Individual		
	T	F	L	T	F	F	L	T	F	L	T	F	F	L	T	F
Plasma PK Concentrations				Y	Y ^[1] ^[2]	Y ^[1] ^[2]	Y				Y	Y ^[1] ^[2]	Y ^[1] ^[2]	Y		
Urine PK Concentrations				Y	Y ^[1] ^[2]	Y ^[1] ^[2]	Y				Y	Y ^[1] ^[2]	Y ^[1] ^[2]	Y		
Plasma PK Parameters	Y			Y			Y	Y			Y					
Urine PK Parameters				Y			Y				Y					

NOTES :

- T = Table, F = Figure, L = Listing, Y = Yes display generated.
- Stats Analysis = Represents TFL related to any formal statistical analyses (i.e. modelling) conducted.
- Summary = Represents TFL related to any summaries (i.e. descriptive statistics) of the observed raw data.
- Individual = Represents FL related to any displays of individual subject observed raw data.

^[1] Linear and Semi-Log plots will be created on the same display.

^[2] Separate mean and median plots will be generated.

8. SECONDARY STATISTICAL ANALYSES

8.1. Safety Analyses

The safety analyses will be based on the “Safety” population, unless otherwise specified.

Table 8 provides an overview of the planned safety analyses with full details of data displays being presented in [Appendix 11: List of Data Displays](#).

Table 8 Overview of Planned Safety Analyses

Display Type	Absolute				Change from Baseline			
	Summary		Individual		Summary		Individual	
	T	F	F	L	T	F	F	L
Exposure								
Extent of Exposure				Y				
Adverse Events								
All AEs	Y			Y				
All Drug-Related AEs	Y			Y				
Serious AEs	Y			Y				
Withdrawal AEs				Y				
Laboratory Values								
Clinical Chemistry				Y	Y			
Hematology				Y	Y			
Urinalysis (Dipstick)	Y			Y				
ECGs								
ECG Findings	Y			Y				
ECG Values				Y	Y			Y
Vital Signs								
Vital Signs				Y	Y			
Liver								
Liver Events [1]				Y				
Cardiovascular								
Cardiovascular [1]				Y				
Clostridium Difficile								
Clostridium difficile Testing [1]				Y				
Rash Events								
Rash Events [1]				Y				

NOTES :

1. Conditional displays, they will only be produced when an event has occurred.
- T = Table, F = Figure, L = Listing, Y = Yes display generated.
- Summary = Represents TFL related to any summaries (i.e. descriptive statistics) of the observed raw data.
- Individual = Represents TFL related to any displays of individual subject observed raw data.

